8.1.4 Adverse Event of Interest

AEIs include anaphylaxis, GI AEs with prolonged dose interruption (> 7 consecutive days) or that result in early discontinuation, accidental and nonaccidental food allergen exposure, severe adverse events, and use of epinephrine. Allergic reactions during food challenges will not be considered related to study product or reported as AEIs.

AEIs will be reported to the Safety Reporting Center within 24 hours of the study site personnel's knowledge of the event, regardless of the investigator assessment of the relationship of the event to study product.

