8.1.4.3 Accidental and Nonaccidental Food Allergen Exposures

An accidental food allergen exposure is any known or suspected exposure to a food to which the subject is allergic, including peanut, whether or not it results in an AE. A nonaccidental food allergen exposure is an intentional exposure to a food to which the subject is allergic, including peanut, whether or not it results in an AE.

Subjects will be instructed to contact the site study coordinator or investigator after any known or suspected food allergen exposure, even if it does not cause symptoms. The subject may be asked to return to the site. These events will be reported as follows:

• The nonserious AEI form will be completed for each of these events, in addition to events where consumption of peanut without a reaction occurs, *unless*:

ARC008 Protocol Amend 6.0

• The accidental/nonaccidental food ingestion safety event meets the definition of an SAE as defined in Section 8.1.3, in which case the SAE form will be completed.

If an accidental/nonaccidental food allergen exposure does not result in an AE, no assessment of severity, seriousness, or relatedness is required.

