8.1.4.4 Severe Adverse Events

Any AE meeting the criteria for severe as defined in Section 8.2.2.1 will be reported as an AEI.

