9.2. ADVERSE EVENTS OF INTEREST

AEIs include anaphylaxis, GI AEs with prolonged dose interruption (> 7 consecutive days) or that result in early discontinuation, accidental and non-accidental food allergen exposure, severe AEs, and use of epinephrine. Allergic reactions during food challenges will not be considered related to study product or reported as AEIs.

A separate data listing and an overall summary of the number of unique treatmentemergent AEIs and treatment-emergent serious AEIs and subject incidence of treatmentemergent AEIs and treatment-emergent serious AEIs meeting various criteria will be presented for the following AEIs: GI AEs leading to disruption of dosing (with prolonged dose interruption > 7 consecutive days or leading to treatment discontinuation), AEs associated with epinephrine use (excluding use for food allergen exposure or food challenges) or anaphylactic reactions (excluding food challenges unless the reaction was serious), serious treatment-related AEs, treatment-related AEs leading to study product discontinuation, and treatment-related AEs that are severe, life-threatening, or fatal.

The overall summary of treatment-emergent AEIs and treatment-emergent serious AEIs will be repeated for the subgroups described in Section 6.3.

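### The SAP 9.2 table labelled AEI does not count the AEI that the protocol and SAP 9.2 define: severe AEs are filtered by relatedness and food-allergen exposures have no category

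*SAP*

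**What the plan says.** Protocol 8.1.4 gives five AEI components. Two are anaphylaxis and GI AEs that interrupt dosing for a prolonged period or end it early; the other three are "accidental and nonaccidental food allergen exposure, severe adverse events, and use of epinephrine". Reactions during food challenges are not AEIs. AEIs go to the Safety Reporting Center within 24 hours, "regardless of the investigator assessment of the relationship of the event to study product". Protocol 8.1.4.4 leaves no room for a relatedness condition on severe events: "Any AE meeting the criteria for severe as defined in Section 8.2.2.1 will be reported as an AEI". Protocol 8.1.4.3 defines an accidental exposure as "any known or suspected exposure to a food to which the subject is allergic, including peanut, whether or not it results in an AE", and treats intentional exposure in the same way.

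The first paragraph of SAP 9.2 repeats these five components, including "accidental and non-accidental food allergen exposure, severe AEs, and use of epinephrine", and the food-challenge exclusion.

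The second paragraph of SAP 9.2 then specifies one listing and one overall summary for a stated list of AEIs:

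- GI AEs that disrupt dosing
- "AEs associated with epinephrine use (excluding use for food allergen exposure or food challenges" (the parenthesis closes there), or anaphylactic reactions, with food-challenge reactions left out unless serious
- "serious treatment-related AEs, treatment-related AEs leading to study product discontinuation"
- "and treatment-related AEs that are severe, life-threatening, or fatal"

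SAP 6.3 repeats this summary for Treatment Pathways 1-3 and 4-5. SAP 13, which lists departures from the protocol, covers change scores and the real world peanut challenge and does not mention AEIs.

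**The concern.** The two paragraphs of SAP 9.2 use the label AEI for two different sets of events. A programmer who follows the second paragraph exactly will produce a table titled as AEIs that does not match the definition directly above it or the one in the protocol.

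This matters because describing safety is the primary objective of an open-label, uncontrolled study, and relatedness is the investigator's opinion (Protocol 8.2.2.2). The protocol made AEI reporting independent of that opinion, and the SAP brings it back as a filter on severe events. Someone who reads the AEI table against the protocol definition would take it to cover all severe AEs and all exposures, which it does not.

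**Working it through.** No arithmetic reproduces or refutes a stated figure, because the plan gives none. The check compares the definition with the tabulated set.

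| Component | Definition (Protocol 8.1.4; SAP 9.2, first paragraph) | AEI listing and summary (SAP 9.2, second paragraph) |
|---|---|---|
| Anaphylaxis | Included; challenge reactions excluded | Included; challenge reactions admitted if serious |
| GI AEs with prolonged interruption or early discontinuation | Included | Included |
| Epinephrine use | Included | Included, but not when given for a food exposure |
| Severe AEs | All | Treatment-related only |
| Food-allergen exposure | All, with or without symptoms | No category |
| Serious treatment-related AEs | Not a component | Added |
| Treatment-related AEs leading to discontinuation | Not a component | Added |

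The tabulated set is therefore neither the defined set nor a subset of it.

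**Epinephrine.** Protocol 8.1.4.5 waives separate reporting of epinephrine used for an exposure because the exposure is already an AEI. SAP 9.2 keeps that exclusion but has no exposure category to receive the event. Take a reaction to an exposure that is treated with epinephrine, is not anaphylaxis, does not disrupt dosing and is judged unrelated to AR101. It falls outside every category of the summary, even if it is severe.

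**Challenge anaphylaxis.** Admitting serious reactions conflicts with the first paragraph of SAP 9.2. It also conflicts with SAP 9.2.1, which excludes challenge reactions from treatment-emergent anaphylaxis.

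**What other sections supply.**
- SAP 9.1 tabulates grade 3 or higher TEAEs without a relatedness limit, TEAEs with epinephrine use, and TEAEs after food-allergen exposure.
- SAP 9.2.3 tabulates food allergy episodes by study period.
- SAP 6.3 names pathway-group repeats of the overall TEAE/TESAE summary, rescue medications, the AEI summary and immunoglobulins. It names none for the grade 3 or higher table or the 9.2.3 table.

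**Size.** Let r be the share of severe AEs judged related, and u the share of unrelated severe AEs that still enter through the anaphylaxis, epinephrine or GI categories, which carry no relatedness filter.
- Share missing from the severe row: 1 − r.
- Share missing from the whole table: (1 − r)(1 − u), which lies between 0 and 1 − r.

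The documents give neither r nor u, so no figure follows. The loss in subject incidence may be smaller, because a subject with one unrelated and one related severe AE is still counted.

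**Direction.** The filter and the missing exposure category can only remove events from those two components. The two added categories and serious challenge anaphylaxis can only add events. The net effect on a combined total is not determined.

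**The case against.** The strongest reply is that nothing is hidden. Severe AEs of any relatedness, AEs after exposure, epinephrine-associated AEs and food allergy episodes each have their own table. Overall AEI incidence is not an endpoint in Protocol section 2 or SAP 3.1; anaphylaxis, epinephrine use, exposures, AEs after exposure and EoE are separate endpoints. The protocol's wording on relatedness governs expedited reporting, not a table, and Protocol 9.7 plans no AEI table. SAP 9.2 states openly which categories its summary covers. Whether the table carries a pooled total depends on the output shells, which are not in the documents. Most of this stands, and it limits the consequence. It does not remove the contradiction, because SAP 9.2 itself defines the term and then tabulates something else under it.

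A reader might infer three stronger things that the documents do not support.

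- *That unrelated severe AEs and exposures go unreported.* They are absent as categories from one listing, one summary and its repeats, and appear in SAP 9.1 and 9.2.3.
- *That the loss can be sized from the EoE cases in Protocol 1.4.1.1.* There 12 of 16 were considered related, so (16 − 12)/16 = 25% were not. But only 2 of the 16 were severe, so this says nothing reliable about severe AEs. In the severe anaphylaxis figures of the same section, 15 of 16 events were triggered by AR101, and anaphylaxis enters the table unfiltered.
- *That the AEI total must look more favourable than it should.* The added categories work the other way, and SAP 7.5 imputes missing relatedness as related and missing severity as severe.

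**Conclusion.** The inconsistency is real, and no other section resolves it. As written, the AEI listing, the overall AEI summary and the repeats for Pathways 1-3 and 4-5 do not report the AEI defined in Protocol 8.1.4, Protocol 8.1.4.4 and the first paragraph of SAP 9.2. SAP 13 does not say so.

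The consequence is limited. No endpoint changes, no data are lost, and the study makes no formal comparisons. The gap is widest in the pathway repeats. SAP 6.3 specifies the AEI summary for the ARC005 children in Pathways 4-5 but no exposure table and no grade 3 or higher table for them. The overall TEAE summary may show some severity counts by pathway group, but the SAP does not name its criteria.

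The severe-AE and exposure components can only be understated, by an amount that cannot be derived from the documents. The direction of any combined AEI total is uncertain. This conclusion assumes that the outputs follow the SAP text. A shell that already includes unfiltered severe AEs and exposures would settle those two parts of the point.

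**What to change.** In the specification of the SAP 9.2 AEI listing and summary, and in the SAP 6.3 pathway repeats:

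1. Change the last category to AEs that are severe, life-threatening or fatal regardless of relatedness, with the treatment-related subset as an indented row.
2. Add a row for accidental and non-accidental food-allergen exposures, drawn from the SAP 9.2.3 data. State whether an exposure without symptoms counts as an episode there.
3. Show serious treatment-related AEs and treatment-related AEs leading to discontinuation outside any AEI total.
4. Reconcile the handling of serious food-challenge anaphylaxis with the opening definition of SAP 9.2 and with SAP 9.2.1.
5. Declare the change as post hoc in the clinical study report. SAP 1.1 restricts Version 2, written after database lock, to Appendix A. SAP 6.1 allows additional analyses if they are documented and identified as post hoc.

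If the narrower table is kept, the least that is needed is a title that does not call it the AEI summary, a statement in the report that it covers a narrower set, and cross-references to SAP 9.1 and 9.2.3.

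The cost is one filter and one row in one table and its repeats, plus the matching listing, from data already collected. The counts of severe AEs and exposures shown as AEIs may be higher.

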9.2.1. Anaphylaxis

Anaphylactic AEs will be considered AEIs. Anaphylaxis is defined by a number of signs and symptoms that occur alone or in combination within minutes up to a few hours after exposure to a provoking agent. The severity of the reaction will be assessed according to the EAACI system for grading the severity of anaphylactic reactions (Muraro, 2007).

All reported anaphylactic reaction episodes will be listed by treatment pathway and subject.

Each anaphylactic reaction will be identified by the following triggers:

• Study product/Investigational product (IP)

- Peanut or peanut-containing food
- Other food allergen
- Medication
- Insect sting
- Environmental allergen(s)
- Other
- Unknown

Treatment-emergent anaphylactic reactions include anaphylactic reactions that occur after first dose of AR101 in ARC008 through 30 days after last dose of study product, but excluding anaphylactic reactions that occur during or related to a food challenge. Treatment-emergent anaphylactic reactions will be summarized in the Safety Population separately for the following study periods:

- Initial Escalation
- Up-Dosing
- Initial and Extended Maintenance
- Overall (Initial Escalation, Up-Dosing, and Initial and Extended Maintenance)

Summaries of each study period will include:

- The number of anaphylactic reactions.
- The number of anaphylactic reactions by trigger, study product, peanut or peanutcontaining food, other food allergen, medication, insect sting, environmental allergen, other and unknown.
- Incidence of subjects experiencing an anaphylactic reaction by number of episodes, subjects experiencing an anaphylactic reaction by severity using modified EAACI guidelines, subjects experiencing an anaphylactic reaction that was a SAE, subjects experiencing an anaphylactic reaction that required epinephrine use, the location of epinephrine episodes (home or study site), and the individual symptoms involved.

The above summary will be produced for all treatment-emergent anaphylactic reactions, all treatment-emergent anaphylactic reactions by total AR101 exposure including parent studies, and for treatment-related anaphylactic reactions. Anaphylactic reactions will also be listed by treatment pathway, subject ID, and episode date.

9.2.2. Gastrointestinal AEs Resulting in Prolonged Interruption of Dosing

GI AEs, typically chronic/recurrent GI AEs, that result in prolonged interruption of dosing will also be considered AEIs and will be assessed longitudinally. To delineate these AEIs, prolonged interruption of dosing is defined as withholding AR101 for > 7 days. This will include 3 categories of subjects:

- Any subject whose dose is withheld for > 7 days due to GI AEs and resumes dosing at a reduced dose level
- Any subject who develops chronic/recurrent GI AEs at or before reaching the 20 mg dose level and resumes dosing after a 30-day dosing hiatus
- Any subject who experienced GI AEs and discontinues early from the study

Subjects who discontinue AR101 treatment early due to chronic/recurrent GI AEs will be requested to return to the clinic for evaluation monthly for at least 6 months (if the subject is asymptomatic, telephone follow-up with a physician investigator may substitute for inclinic visit, at the investigator's discretion). If chronic/recurrent GI AEs persist beyond 6 months, subjects will continue to be followed with monthly clinic visits (telephone follow-up with an investigator may substitute for inclinic visit, at the investigator may substitute for inclinic visit, at the investigator may substitute for inclinic visit, at the investigator's discretion) until the symptoms have resolved or are assessed to have stabilized with optimal medical management.

If chronic/recurrent GI AEs do not completely resolve within 6 weeks after discontinuation of AR101 dosing, the subject should be referred to a (pediatric) gastroenterologist. Subjects with EoE confirmed by biopsy will have safety follow-up monthly for at least 6 months or until resolution of symptoms and/or tissue eosinophilia, whichever is last.

9.2.3. Accidental and Non-accidental Food Allergen Exposures

An accidental food allergen exposure is any known or suspected exposure to a food to which the subject is allergic, including peanut, whether or not it results in an AE. A non-accidental food allergen exposure is an intentional exposure to a food to which the subject is allergic, including peanut, whether or not it results in an AE.

The non-serious AEI form will be completed for each of these events, in addition to events where consumption of peanut without a reaction occurs, unless the accidental/non-

accidental food ingestion safety event meets the definition of an SAE as defined in Section 8.1.3 of the protocol, in which case the SAE form will be completed.

If an accidental/non-accidental food allergen exposure does not result in an AE, no assessment of severity, seriousness, or relatedness is required. Treatment-emergent food allergy episodes include food allergy episodes that occur after first dose of AR101 in ARC008 through 30 days after last dose of study product, but excluding food allergy episodes that occur during or related to a food challenge.

These treatment-emergent food allergy episodes will be summarized by study period:

- Initial Escalation
- Up-dosing
- Initial and Extended Maintenance
- Overall (Initial Escalation, Up-Dosing, and Initial and Extended Maintenance)

For each period, the number of subjects experiencing any food allergy episode, the number of subjects experiencing a food allergy episode in response to peanut (or non-peanut), the number of subjects experiencing an accidental (or non-accidental) food allergy episode, the number of episodes of each (peanut-related, non-peanut related, accidental, and non-accidental) experienced per subject, and the total number of food allergy episodes (peanut-related, non-peanut related, non-peanut related, accidental) will be summarized. In addition, the number of episodes considered SAEs, those that required treatment, and those that required epinephrine use will also be summarized.

All reported food allergy episodes will be listed by treatment pathway and subject.

9.2.4. Adverse Events Associated with Use of Epinephrine

AEs may result in epinephrine use. Upon awareness of such an event, site staff will report it within 24 hours using the AEI form, independent of severity or relatedness, or whether it was administered at the study site or at home. If the epinephrine was used for an allergic reaction that meets criteria for anaphylaxis, an accidental/non-accidental food allergen exposure, a severe AE, or an SAE, the use need not be reported separately. The intent of this AEI is to record events that do not fall into one of the other categories.

9.3. LABORATORY DATA

Blood samples will be collected at the visits identified in the schedules of events in the appendices of the protocol after the predose vital signs and PEF and before administration of AR101.

All sexually active females of childbearing potential will undergo a serum pregnancy test at Screening and urine pregnancy testing at the visits indicated in the schedules of events in the appendices of the protocol.

Laboratory data (hematology, blood sample collection, and pregnancy test results) and abnormal laboratory values will be listed by treatment pathway, subject ID, and visit.

9.4. VITAL SIGNS

Vital signs (blood pressure [BP], pulse rate, and body temperature) will be measured at the visits indicated in the schedules of events in the appendices of the protocol. For Treatment Pathways 4 and 5, vital signs also include respiratory rate and oxygen saturation level. Measurement of BP and pulse rate should be preceded by at least 5 minutes of rest for the subject.

Vital signs (temperature, heart rate, respiratory rate, systolic/diastolic blood pressure, and oxygen saturation) will be listed by treatment pathway, subject ID, and visit.

9.5. PHYSICAL EXAMINATION

Complete and abbreviated (symptom-directed) physical examinations will be conducted at the visits indicated in the schedules of events in the appendices of the protocol. Height and weight will be recorded as part of a complete physical exam. Physical examination results will be listed by treatment pathway, subject ID, and visit. BMI will be included in the listing and calculated as [weight (kg)]/[height (cm)/100]².

9.6. PEDIATRIC EOSINOPHILIC ESOPHAGITIS SYMPTOM SCORES

Subjects with GI AEIs will be asked to complete the Pediatric Eosinophilic Esophagitis Symptom Scores (PEESS) v2.0 questionnaire (Franciosi, 2011) while they are symptomatic, at the End of Treatment visit, and then monthly for 6 months thereafter. Parents/caregivers will also complete the PEESS v2.0 as appropriate. Subjects who discontinue AR101 treatment early due to chronic/recurrent GI AEs will return to the clinic for evaluation monthly for at least 6 months. If the subject is asymptomatic, telephone follow-up with an investigator may substitute for in-clinic visit, at the investigator's discretion. If chronic/recurrent GI AEs persist beyond 6 months, subjects will continue to be followed up with monthly clinic visits (telephone follow-up with an investigator may substitute for in-clinic visit, at the investigator may substitute for in-clinic visit, at the investigator's discretion) until the symptoms are resolved or stable with optimal medical management or the investigator considers them irreversible, in which case the sponsor must be notified.

The PEESS questionnaire is composed of 20 items investigating the frequency and severity of EoE symptoms in the last month. The total score consists of all 20 items. The frequency of symptoms is assessed by items 1, 3, 5, 7, 9, 11, 13, 15, 17, 19 and 20, where each item is scored as: 0=Never, 1=Almost never, 2=Sometimes, 3=Often, 4=Almost always. The

severity of symptoms is assessed by items 2, 4, 6, 8, 10, 12, 14, 16, and 18, where each item is scored as: 0=Not bad at all, 1=A little bad, 2=Kind of bad, 3=Bad, 4=Very bad. Each item score is transformed to 0-100 as follows: 0=0, 1=25, 2=50, 3=75, 4=100.

The total, frequency total, and severity total scores are computed as the sum of the items divided by the number of items answered. If more than 50% of the items for the calculation of a score are missing, the score will not be calculated.

All PEESS data (collected from subjects and parents/caregivers) will be listed, including the frequency total, severity total, and total scores.

9.7. PEAK EXPIRATORY FLOW

The PEF should be measured at approximately the same time of day at each visit (eg, morning, afternoon, evening). The PEF will be measured in triplicate using a hand-held device at the visits indicated in the schedules of events in the appendices of the protocol. The subject will be asked to stand and forcefully blow into the device 3 times.

PEF results will be listed by treatment pathway, subject ID, and visit.

9.8. ASTHMA CONTROL TEST AND THE CHILDHOOD ASTHMA CONTROL TEST QUESTIONNAIRE

The ACT or C-ACT will be administered only to subjects with known asthma at the visits indicated in the schedules of events in the appendices of the protocol during each visit and prior to the measurement of lung function.

The ACT (Schatz, 2006) is a self-administered 5-item questionnaire for subjects 12 years of age or older. It assesses the level of asthma control during the prior 4 weeks. Specifically, the test asks about shortness of breath, general asthma symptoms, use of rescue medications, the effect of asthma on daily functioning, and the overall self-assessment of asthma control. Each question is scored with a 5-point scale, with lower numbers equating to worse control. The scores for each question are totaled, and a composite score of more than 19 indicates well-controlled asthma. Missing data will not be imputed. If any of the 5 questions have a missing response, the total ACT score will not be calculated. Subjects who have turned 12 since entry into the ARC008 study will be asked to complete the ACT.

The C-ACT (Liu, 2007) is a 7-item questionnaire for subjects aged 4 to 11 years. It assesses the control of asthma during the prior 4 weeks. The child completes the first part, which has 4 questions and with a choice of 4 responses to each question. The child should read and respond to each question. If the child needs assistance with reading or understanding the question, the parent/caregiver may help; however, only the child should pick a response to the question. The parent/caregiver completes the second part, which has 3 questions with a choice of 6 responses ranging from 0 (worse asthma) to 5 (controlled asthma) for each question. The sum of all the responses to the questions provides a score

that ranges from 0 (very poor control) to 27 (well-controlled asthma) with a score of more than 19 indicating asthma that is well controlled.

Listing of the results from each questionnaire, including the total score will be provided, sorted by treatment pathway, subject ID, and visit.

